8.14.3	Payments to subject for time, effort and inconvenience (i.e. compensation)	33
8.14.4	Gifts	33
9	PUBLICATION	33
10	REFERENCES	34

ABBREVIATIONS AND DEFINITIONS OF TERMS

AHI	Obstructive apnea hypopnea index
AT	Adenotonsillectomy
CPAP	Continuous positive airway pressure
NCS	Nasal corticosteroids
OSA	Obstructive sleep apnea syndrome
PSG	Polysomnogram

ABSTRACT

Context:

The childhood obstructive sleep apnea syndrome (OSAS) is very common, occurring in 1-3% of otherwise healthy children. If untreated, it can result in significant morbidities. Current treatment of childhood OSAS is primarily surgical (i.e., adenotonsillectomy, AT), with continuous positive airway pressure (CPAP) and other medical measures being used much more rarely. Several studies have suggested that nasal corticosteroids (NCS) may be effective in the treatment of childhood OSAS. However, the utility of NCS in children with OSAS has not been fully evaluated.

Objectives:

Primary Objective: To determine the efficacy of NCS vs. placebo in treating OSAS in children.

Secondary Objectives:

- To determine which factors modify the response to NCS
- To determine the long-term effect of NCS vs. placebo in the treatment of OSAS in children
- To determine the side-effects associated with chronic NCS use in children with OSAS

Study Design: Randomized, parallel, double-blind, placebo-controlled study.

Setting/Participants: Single site study to be performed at CHOP. Participants will be recruited from outpatient offices and all procedures will be performed during outpatient research visits. 318 children aged 5-12 years with mild to moderate OSAS will be recruited.

Study Interventions and Measures:

Participants will be randomized to a 3-month course of nasal fluticasone or placebo. Both groups will undergo the following procedures at baseline and 3 months: history and physical exam, sleep study, pediatric sleep questionnaire, nasal symptoms questionnaire, quality of life questionnaire, neurobehavioral testing, acoustic reflectance airway measurement, spirometry, percutaneous skin allergy test, nasal secretions genetic expression profile, nasal secretions biomarkers, blood work for systemic biomarkers, cortisol, DHEAS, and ACTH levels, ophthalmology exam, knee height measurement and DXA scan. Families will keep an infection log. At the 3 months visit, participants in the NCS group will be further randomized to 9 months of NCS or placebo. All measurements will be repeated at the end of this 9-month period.

The primary study outcome measure is the change in OSAS severity measured by the obstructive apnea hypopnea index (AHI) 3 months after randomization.

PROTOCOL SYNOPSIS

Study Title	Utility of nasal steroids for treatment of childhood obstructive sleep apnea
Funder	NHLBI
Clinical Phase	N/A
Study Rationale	
 • The childhood obstructive sleep apnea syndrome (OSAS) is very common, occurring in 1-3% of otherwise healthy children. If untreated, it can result in significant morbidity. • In vitro, nasal corticosteroids (NCS) have been shown to reduce tissue proliferation and increase apoptosis in adenotonsillar tissue. These studies provide biologic plausibility for the use of NCS in the treatment of children with OSAS and adenotonsillar hypertrophy. • Current treatment of childhood OSAS is primarily surgical (i.e., adenotonsillectomy, AT), with continuous positive airway pressure (CPAP) and other medical measures being used much more rarely. AT is efficacious but residual OSAS often remains, and CPAP use is limited by poor adherence. • Several studies have suggested that NCS may be effective in the treatment of childhood OSAS. However, these studies have been limited by factors such as small size, lack of randomization and blinding, short-term follow-up, involvement of children with only very mild OSAS, and/or lack of stratifying for the presence of atopy. • We therefore plan a randomized controlled trial evaluating the efficacy and safety of NCS vs. placebo in children with mild to moderate OSAS. Our overall hypothesis is that NCS will be safe and efficacious in the treatment of mild to moderate childhood OSAS, particularly in children with asthma/atopy, but will require ongoing maintenance therapy.
Study Objective(s)	
Primary
 
To determine the efficacy of NCS vs. placebo in treating OSAS in children
 
Secondary
 
 • To determine which factors modify the response to NCS • To determine the long-term effect of NCS vs. placebo in the treatment of OSAS in children

	
 • To determine the side-effects associated with chronic NCS use in children with OSAS
Test Article(s) (If Applicable)	
 • Fluticasone nasal spray (55 mcg [one spray] per nostril daily) is chosen as in vitro studies have shown that it has greater potency in reducing adenotonsillar cellular proliferation than budesonide or dexamethasone. • Fluticasone is FDA-approved for the study age group. The Investigational Drug Service will prepare blinded nasal spray bottles with a metered pump (to deliver 55 mcg/0.1mL or placebo/0.1mL per pump) with a 30 day supply of solution per bottle.
Study Design	
 • Randomized, parallel, double-blind, placebo-controlled study.
Subject Population key criteria for Inclusion and Exclusion:	
Inclusion Criteria
 
 1. Subjects age 5-12 years. 2. Mild to moderate OSAS, defined as an obstructive apnea index (AI) of 1-20/hr of total sleep time (TST) or AHI 2-30/hr of TST. 3. Parent-related symptoms of habitual snoring (>3 nights per week). 4. No history of adenotonsillectomy or prior NCS use. 
Exclusion Criteria
 
 1. Severe OSAS or significant hypoxemia or hypercapnia on polysomnography (PSG), such that definitive treatment should not be delayed (AHI > 30/hr, more than 2% total sleep time with SpO₂ <90%, end-tidal PCO₂ > 60 mm Hg for \geq 5 minutes, pathologic arrhythmias). 2. History of recurrent throat infections 3. Any NCS use in the past 3 months, or NCS use for \geq 2 weeks in the past year 4. Abnormalities on baseline safety screening tests 5. Previous adenotonsillectomy 6. Previous adenoidectomy unless adenoidal tissue has been documented to have regrown 7. CPAP therapy 8. Pregnancy
Number Of Subjects	
 • 318 children will be recruited at CHOP. This is a single center study

Study Duration	
 • The participation of subjects randomized to the placebo group at the baseline visit will be 3 months. • The participation of subjects randomized to the NCS group at the baseline visit will be 12 months. • The entire study is expected to last 5 years
Study Phases	(1) Screening : screening for eligibility and obtaining consent and
Screening	(2) Intervention : Randomization: placebo or NCS for 3 months
Study Treatment	(3) Follow-up : randomization of NCS group to placebo or
Follow-Up	continuation of NCS for 9 months
Efficacy Evaluations	Change in AHI in the placebo and NCS groups at 3 months of therapy; and at 12 months of therapy
Pharmacokinetic Evaluations	N/A
Safety Evaluations	Worsening symptoms of OSAS, such as daytime sleepiness or development of complications, such as failure to thrive,
Statistical And Analytic Plan	
 • It is assumed that 50% of subjects will fail the baseline screening PSG. Thus, 318 subjects will be recruited initially. • 159 eligible subjects will be randomized in a 2:1 fashion to NCS vs. placebo, respectively; the initial group sizes will therefore be 106 NCS vs. 53 placebo subjects. The 2:1 randomization ratio is to allow for further randomization during the follow-up phase of the study. Based on our past studies we will assume a drop-out rate of 5% at 3 months. Therefore, the available sample size for analysis for Aim 1 will be 100 NCS vs. 50 placebo subjects. • All analyses will be conducted with Stata 13.0, with two-sided tests of hypotheses and a p-value < 0.05 as the criterion for statistical significance. • Analyses will be conducted according to the intent to treat principle, with subjects analyzed according to their initial treatment assignment. • Descriptive analyses will include computation of means (with 95% confidence intervals), standard deviations, medians, interquartile-ranges (IQR) of continuous variables and tabulation of categorical variables. • A two-group t-test for independent samples or Wilcoxon rank sum test will be used to test the primary hypothesis that

the changes in AHI are equal between the two treatment groups.

[figure not shown]
DATA AND SAFETY MONITORING PLAN

Participants' data will be closely monitored by an external Data Safety Monitoring Board (DSMB) and an external safety officer. They will monitor adverse events and treatment failures.

TABLE 1: SCHEDULE OF STUDY PROCEDURES

Percutaneous skin allergy test		X												
Blood tests		X			X									X
Ophthalmology exam		X			X									X
Nasal secretion testing		X			X									X
DXA scan		X			X									X
Urine pregnancy test		X			X									X
Randomization		X			X									
Dispense Study Drug		X			X									
Drug Compliance					X		X				X			X
Adverse Event Assessment		X	X	X	X	X	X	X	X	X	X	X	X	X

FIGURE 1: STUDY DIAGRAM

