3.2 Allocation to Treatment Groups and Blinding

Randomization: A blocked randomization scheme (with block sizes that vary randomly between 2 and 4) will be employed to initially randomize subjects to NCS or placebo at baseline; the same approach will then be employed for the re-randomization at 3 months, when the subjects who were initially randomized to receive NCS will be re-randomized in equal numbers to receive NCS or placebo. The randomization will be stratified according to atopy/asthma, current use of inhaled corticosteroids for asthma (yes/no), obesity status and seasonality (spring/summer vs autumn/winter). Programs will be written in Stata to conduct the randomization, and the assignments will be stored in sealed envelopes stored in a locked cabinet that is only accessible to CTSA staff who are not affiliated with other aspects of the

study.

Blinding: The study will be double-blinded. All subjects, their families, investigators and study team members will be blinded, except for one research coordinator. In order to avoid bias and equipoise shifting, two research coordinators will be part of this study. One of them will be responsible for enrolling subjects and will be blinded to the treatment allocation status. The other research coordinator will be responsible for breaking the blind at the 3 month visit. She will refer participants allocated to placebo to clinical care, and communicate with the statistician regarding the randomization of participants initially allocated to NCS. Other investigators will evaluate research data (e.g., read polysomnograms) that are deidentified and coded to prevent becoming unblinded. Note that there is no physical exam after the baseline study. The statistician will generate a list of random numbers for study arm assignment, and a CTSA staff member who is not otherwise involved in the study will provide the drug/placebo.

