6 STATISTICAL CONSIDERATIONS

6.1 Primary Endpoint

The primary endpoint is the change in AHI at the 3-month visit.

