6.3.2 Efficacy Analysis

The primary analysis will be based on an intention to treat approach and will include all subjects randomized at Visit 1.

The primary efficacy endpoint will be the change in AHI between Randomization and Visit 2.

Secondary endpoints will include the change in AHI at the 12-month visit in each group and the change in knee height, bone health, adrenal suppression, ocular health and infection at 12 months.

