6.4 Sample Size and Power

Sample size for primary endpoint:

All sample size calculations were conducted using nQuery Advisor software. It is assumed that 50% of subjects will fail the baseline screening PSG. Thus, 318 subjects will be recruited initially. 159 eligible subjects will be randomized in a 2:1 fashion to NCS *vs* placebo, respectively; the initial group sizes will therefore be 106 NCS *vs* 53 placebo subjects. The 2:1 randomization ratio is to allow for further randomization for Aim 3. Based on our past studies (see *Preliminary Data*), we will assume a drop-out rate of 5% at 3-months. Therefore, the available sample size for the primary endpoint analysis will be 100 NCS *vs* 50 placebo subjects. This is powered on a comparison of mean changes in AHI between NCS *vs* control subjects at 3-months, based on two prior studies (13, 15). The effect-size for the difference in mean changes between treatment groups for the Brouillette study, calculated as the absolute value of the difference in group means, divided by the pooled estimate of the SD of changes, was 0.87 (15), and for the Kheirandish-Gozal study was 1.75.(13) A two group t-test with a 0.050 two-sided significance level will have $\geq 99\%$ power to detect the effect size of 0.865 (observed in (13)) when the sample sizes in the two groups are 100 and 50, respectively. In addition, the two group t-test will also have $>99\%$ power to detect the effect size of 1.75 that was observed in (15). We will therefore have excellent power to determine treatment group differences of the magnitude observed by these past studies. However, as the effect sizes were so different for these two studies, and as the current study will include a more heterogeneous population, e.g., children with more severe OSAS, the observed effect-size may be smaller. If so, we will have 81% power to detect an effect size of 0.50. An effect-size of 0.50 corresponds to a mean reduction in AHI of 4.2/hr in the NCS group and no change in the placebo group, assuming the SD of changes is 8.4 (as observed in (13)); and an AHI reduction of 1/hr with NCS (and no change in placebo) if the SD of change is 2 as observed in (15). Any smaller difference between groups with respect to changes in AHI would not be clinically meaningful. We are therefore well-powered to detect meaningful changes for the primary endpoint.

Sample size for secondary endpoints:

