Comparison of the changes in AHI at 12 months: For this endpoint, the 100 remaining NCS subjects (assuming there were ~6 dropouts) at 3-months will be re-randomized in equal numbers to continued NCS or placebo. Assuming a conservative drop-out rate of 10%, there will be 45 evaluable subjects per treatment group at 12 months. We anticipate that subjects treated with NCS will continue to improve (i.e., have continued reductions in AHI), while those on placebo will have a worsening of their condition (i.e., increases in AHI). We anticipate that subjects who continue on NCS will have similar (or greater) improvements during the additional 9 months of follow-up as were observed during the first 3 months of treatment. Assuming that NCS subjects have a mean reduction in AHI of 4/hr, while placebo subjects have a mean increase of 3/hr, a two-sample t-test will have 97% power to detect this difference, assuming that the common SD of changes is 8.4 (as in (15)); if the SD of changes is 2.0 (as in (13)), then we will have >99% power. However, if the observed differences of the current study are smaller, a sample size of 45 in each group will have 80% power to detect an effect size of 0.597; this would be observed if the mean reduction in AHI is 2.4/hr for subjects treated with NCS, *vs* no change for subjects treated with placebo, assuming a SD of 4.0(13).

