8.8 Treatment Assignment Methods

8.8.1 Randomization

A blocked randomization scheme (with block sizes that vary randomly between 2 and 4) will be employed to initially randomize subjects to NCS or placebo at baseline; the same approach will then be employed for the re-randomization at 3 months, when the subjects

who were initially randomized to receive NCS will be re-randomized in equal numbers to receive NCS or placebo. An exception for this randomization schedule will be siblings. Specifically, siblings will be randomized to the same arm to avoid parental confusion with study drug administration. For example, parents may confuse study drug with placebo because both study drug and placebo look, taste and smell identical and parents may give the wrong medication to their children. The randomization will be stratified according to atopy/asthma, current use of inhaled corticosteroids for asthma (yes/no), obesity status and seasonality (spring/summer *vs* autumn/winter). Programs will be written in Stata to conduct the randomization, and the assignments will be stored in sealed envelopes stored in a locked cabinet that is only accessible to CTSA staff who are not affiliated with other aspects of the study.

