- On a quarterly basis, or more frequently if needed, summary reports of all AEs, SAEs, Urgent/Immediate Medical Referrals, and Treatment Failures by treatment arm also will be provided to the DSMB

- For each DSMB meeting, reports will be provided. These will include data on recruitment and baseline characteristics, pooled data on eligibility violations, completeness of follow-up and compliance, analyses of primary and secondary efficacy endpoints, subgroup and adjusted analyses, analyses of AEs and symptom severity, and analyses of laboratory data. The study statistician will prepare these reports.
- The reports will provide information that is accurate, with follow-up that is complete to within one month of the date of the DSMB meeting. The Reports will be provided to DSMB members approximately one week prior to the date of the meeting.
- Minutes for each meeting will be prepared

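### The primary comparison of 3-month AHI change adjusts for neither baseline AHI nor the four stratification factors, and the choice between t-test and Wilcoxon is left open

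*Combined protocol and SAP*

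**What the plan says.** - **Endpoint.** Section 6.1: "The primary endpoint is the change in AHI at the 3-month visit". Section 6.3.2: "The primary efficacy endpoint will be the change in AHI between Randomization and Visit 2". Section 6.3.2 also sets an intention-to-treat population but names no test, model or covariate.
- **Test.** Only the Protocol Synopsis (Statistical And Analytic Plan) names one: "A two-group t-test for independent samples or Wilcoxon rank sum test will be used to test the primary hypothesis that" the two arms have equal AHI changes. There is no default, no distributional check and no covariate.
- **Power.** Section 6.4: "This is powered on a comparison of mean changes in AHI between NCS" and placebo, using a two-group t-test. That is a planning assumption and does not say which test decides the trial.
- **Stratification.** Section 3.2: "The randomization will be stratified according to atopy/asthma, current use of inhaled corticosteroids for asthma (yes/no), obesity status and seasonality (spring/summer vs autumn/winter"); section 8.8.1 repeats this. No primary analysis text uses these factors.
- **Adjustment.** It is mentioned once, in the list of DSMB report contents in section 8.11.1: "analyses of primary and secondary efficacy endpoints, subgroup and adjusted analyses". No covariates are given and there is no link to the primary test.
- **12 months.** The only analysis mentioned is in the power text of section 6.4, where "a two-sample t-test will have 97% power to detect this difference". It is also unadjusted.

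**The concern.** There are two separate problems.

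**Precision.** A change score subtracts baseline AHI with the slope fixed at 1. If the true slope is below 1, some baseline variation stays in the error term and the treatment estimate is noisier than it need be. In addition, when randomisation is stratified on prognostic factors and the analysis ignores them, the standard error is too large and the test is conservative. Section 6.4 itself warns that the effect may be smaller than in the two past studies.

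**An open choice of test.** The t-test compares mean changes, and the Wilcoxon test compares ranks. Section 6.4 defines a meaningful effect as a mean difference (4.2/hr or 1/hr), so the two tests do not answer the same question. Section 6.5 rules out an interim analysis, yet section 8.11.1 has the study statistician prepare primary-endpoint analyses for DSMB meetings held twice a year. A test not fixed before the first such report could be chosen after outcome data have been seen.

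**Working it through.** **Inputs from the plan:** 100 NCS and 50 placebo analysed, two-sided 0.05, standardised effect d = 0.50, stated power 81% (6.4); 45 against 45 at 12 months, d = 0.597, stated power 80% (6.4); 31% atopic and 34% obese (6.4).

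**Assumed, because the documents do not give them:** r, the baseline to follow-up correlation of AHI; k, the follow-up to baseline SD ratio; the share of variance that the strata explain; and the simulation inputs below.

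**1. The plan's own figure.** Noncentrality = 0.50 / √(1/100 + 1/50) = 0.50 / 0.1732 = 2.887. With 148 df, power is 81.8%, so the stated 81% holds.

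**2. Adjusting for baseline AHI, closed form.** Residual variance relative to the change score is k²(1 − r²) / (1 + k² − 2rk). With k = 1 this is (1 + r)/2. Divide d by the square root of the ratio and use 143 df (baseline plus four factors).

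| k | r | Variance ratio | Power |
|---|---|---|---|
| 1 | 0.3 | 0.65 | 94.5% |
| 1 | 0.5 | 0.75 | 91.2% |
| 1 | 0.7 | 0.85 | 87.5% |
| 1 | 0.9 | 0.95 | 83.7% |
| 0.8 | 0.3 | 0.502 | 98.2% |
| 0.8 | 0.9 | 0.608 | 95.7% |
| 1.25 | 0.8 | 1.000 | 81.8% |
| 1.5 | 0.7 | 0.998 | 81.9% |

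The gain vanishes when the slope rk is near 1, as in the last two rows. The lost degrees of freedom alone cost 81.81% − 81.79% = 0.02 points.

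**3. Simulated AHI-like data** (10,000 trials per cell). Baseline is log-normal (median 6.5, log SD 0.75) truncated to 2–30, and the strata are not prognostic. A: log-scale slope 0.6, log error SD 0.7, 35% relative reduction. B: slope 1, error SD 5, effect 2.5/hr. C: slope 0.6, error SD 4, effect 2.2/hr. Follow-up AHI is floored at 0 in B and C.

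| Power (%) | Pooled t | ANCOVA, ordinary SE | HC2 | HC3 |
|---|---|---|---|---|
| A | 78.7 | 84.2 | 80.9 | 79.2 |
| B | 78.1 | 77.1 | 75.9 | 74.3 |
| C | 76.1 | 87.0 | 86.6 | 85.5 |

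With HC2 the change against the t-test is +2.2 (A), −2.2 (B) and +10.5 (C) points. In A the SD of change differs by arm (8.2 placebo, 6.1 NCS). There, 95% interval coverage is 91.4% with ordinary errors, 93.4% with HC2 and 94.0% with HC3.

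**4. Open choice of test, same scenarios.** Type I error is 4.5–5.1% if a normality test makes the choice and 5.9–6.7% if the smaller p-value is reported. With a real effect, the two tests disagree on p < 0.05 in 11.7% (A), 6.3% (B) and 6.2% (C) of trials.

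**5. Ignoring the strata.** Simulation of stratified blocks of 3 in 12 feasible strata, with 159 randomised, about 150 analysed and 20,000 runs. Assumed: 40% of atopic children on inhaled steroid and half of the children in each season.

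| Variance of change explained by strata | Unadjusted type I error | Power unadjusted | Power adjusted |
|---|---|---|---|
| 0% | 4.9% | 81.4% | 81.2% |
| 10% | 4.3% | 83.0% | 85.6% |
| 20% | 3.1% | 83.8% | 89.2% |
| 30% | 2.4% | 85.2% | 92.7% |

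The plan's own interaction scenario gives one reference point: −6/hr in atopic and −3/hr in non-atopic NCS children, no change on placebo, SD 2.8. Averaged over 2:1 arms the atopy main effect is (2/3) × 3 = 2/hr. It explains 0.31 × 0.69 × 2² = 0.86 of a within-arm variance of 2.8² + (2/3) × 0.31 × 0.69 × 3² = 9.12, or about 9%.

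**6. 12 months** (45 against 45, d = 0.597). Unadjusted power with 88 df is 80.0%. ANCOVA with 83 df and k = 1 gives 93.5%, 89.8%, 85.9% and 81.9% at r = 0.3, 0.5, 0.7 and 0.9, and 80.7% at k = 1.25, r = 0.7.

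**The case against.** The unadjusted t-test on change is a legitimate analysis of a randomised trial. It is unbiased, its stated power is right, and ignoring the strata makes it conservative rather than liberal. Section 6.4 calls anything below d = 0.50 not clinically meaningful, so the plan meets its own target. The largest closed-form gains need k at or below 1, whereas entry is restricted to AHI 2–30 and follow-up is not, which tends to push k up. In the simulated placebo arms k is about 1.61 (A), 1.27 (B) and 0.92 (C), so only C resembles the favourable rows. The plan treats atopy and obesity as modifiers of NCS response, not as predictors of change in both arms. Covariates that predict nothing also cost more than their degrees of freedom: under simple randomisation, five of them took simulated power from 82.0% to 80.5%. Finally, 6.4 powers the t-test and the synopsis lists it first, so the intended default can be guessed.

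Much of this stands as a limit on size. The figures above 90% should not be taken as the expected gain, the roughly 9% for atopy supports the precision argument but not the type I argument, and adjustment can lose a little. None of it supplies a rule for choosing the test: a guessed default is not a pre-specified one. Nor does it remove the case for using a baseline that is already measured and factors that already govern allocation.

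**Conclusion.** The concern holds. The primary comparison is unadjusted, and the deciding test is not fixed anywhere. There is no bias and no power shortfall. What is lost is precision, of uncertain size because r, k and the prognostic strength of the strata are not in the documents. With HC2 errors the simulated change in power runs from about −2 to +10 points, and the closed form runs from no gain to more than 10 points. The open test choice is a modest problem but a real one, with type I error up to 6.7% only if the smaller p-value is taken. This is an improvement the plan should make, with medium confidence in its size.

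**What to change.** In 6.3.2 and the synopsis, name one primary analysis before any comparative data are seen, including the first DSMB efficacy report. The preferred choice is ANCOVA of 3-month AHI (events/hr) on treatment, baseline AHI and main effects of the four stratification factors, reporting the adjusted mean difference with its 95% confidence interval. Fix the type of standard error in advance. HC2 is a reasonable middle choice: it loses less power than HC3 and covers better than ordinary errors in the skewed scenario. Make the unadjusted t-test and the Wilcoxon test on change sensitivity analyses. State a 12-month analysis of the same form, with month-3 AHI and the re-randomisation strata as covariates.

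If the team prefers the unadjusted t-test, naming it in 6.3.2 as the single primary test closes the choice gap but leaves the precision gain unused.

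The cost is wording in 6.3.2 and the synopsis, plus a matching sentence in 6.4 so that the power text describes the named test. All covariates for the primary model are known at randomisation, and the endpoint, scale, visits and sample size do not change. The downside arises if the baseline slope is near 1 and the strata are not prognostic: simulated power then falls by about 1 point with ordinary errors, 2 with HC2 and 2.5 to 3.7 with HC3.
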